### **5.5.2.6 National Institutes of Health Stroke Scale**

NIHSS data is collected at V1a (the worst total NIHSS score post-stroke until V1b is collected), V2, V3, V5, V7 and EOT or EDV and, if applicable, UNS.

The NIHSS is a systematic assessment tool that provides a quantitative measure of stroke-related neurologic deficits. The stroke scale is valid for predicting lesion size and can serve as a measure of stroke severity. A trained investigator or a qualified delegate will record the patient's ability to answer questions and perform activities on the level of consciousness, extraocular movement, visual fields, facial muscle function, extremity strength, sensory function, coordination (ataxia), language (aphasia), speech (dysarthria), and hemi-inattention (neglect). The sum of all 15 individual scores will provide the patient's total NIHSS score where 0 is "no stroke symptoms" and 42 is "severe stroke" [5].

Stroke severity will be stratified based on NIHSS total score as follows:

<11 – mild and moderately severe  
≥11 – severe.

The following questions will be asked:

- 1a. Level of Consciousness (LOC) (scored as 0, 1, 2, 3)
- 1b. LOC Questions (scored as 0, 1, 2)
- 1c. LOC Commands (scored as 0, 1, 2)
2. Best Gaze (scored as 0, 1, 2)
3. Visual (scored as 0, 1, 2, 3)
4. Facial Palsy (scored as 0, 1, 2, 3)
- 5a. Motor Arm (Left Arm) (scored as 0, 1, 2, 3, 4)
- 5b. Motor Arm (Right Arm) (scored as 0, 1, 2, 3, 4)
- 6a. Motor Leg (Left Leg) (scored as 0, 1, 2, 3, 4)
- 6b. Motor Right (Right Leg) (scored as 0, 1, 2, 3, 4)
7. Limb Ataxia (scored as 0, 1, 2)
8. Sensory (scored as 0, 1, 2)
9. Best Language (scored as 0, 1, 2, 3)
10. Dysarthria (scored as 0, 1, 2)
11. Extinction and Inattention (formerly Neglect) (scored as 0, 1, 2)

For each patient, the total NIHSS score at baseline and each post-baseline visit will be calculated adding the individual scores from each item.

The NIHSS score and its change from baseline at each time of examination will be summarised by means of descriptive statistics. Differences between the treatment groups (ESL-Placebo) will be evaluated exploratively using the Wilcoxon-Mann-Whitney Test and exact Hodge-Lehmann CIs at each time of examination (if the SAS code runs for more than 10 minutes, maxtime=50 will be used and the approximate result will be tabulated. A higher maxtime does not lead to a change of the result).

Cumulative incidence of USs will be illustrated using Kaplan-Meier curves by the NIHSS baseline categories (<11, ≥11) and treatment group. Patients without an event or lost to follow-up will be censored at their last visit or termination date. Time to event will be calculated from time of examination since randomisation to first US.

The following statistical outputs will be presented:

[Table 15.2.7.1.1 Summary of NIHSS Total Score – Full Analysis Set](#)

[Table 15.2.7.1.2 Summary of NIHSS Total Score – Per-Protocol Set](#)

The default summary statistics for the NIHSS total score will be presented by treatment group by visit slots at Baseline, V2, V3, V5, V7, EOT, EDV (if applicable) and Endpoint.

[Table 15.2.7.2.1 Analysis of NIHSS Total Score Differences – Full Analysis Set](#)

[Table 15.2.7.2.2 Analysis of NIHSS Total Score Differences – Per-Protocol Set](#)

The Hodges-Lehmann estimate of location shift and the corresponding 95% CIs including the p-value will be presented by visit slots for V3, V5, V7 and Endpoint for ESL-Placebo.

Figure 15.2.3.1 Cumulative Incidence Curves of Unprovoked Seizures using Kaplan-Meier Curves by NIHSS Total Score – Full Analysis Set

Figure 15.2.3.2 Cumulative Incidence Curves of Unprovoked Seizures using Kaplan-Meier Curves by NIHSS Total Score – Per-Protocol Set

Cumulative incidence curves of USs using Kaplan-Meier curves displayed by time after randomisation and treatment group for each category of the NIHSS total score.

Listing 16.2.3.4 National Institutes of Health Stroke Scale (NIHSS) – Enrolled Set

The NIHSS items and total score data will be listed by treatment group.

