This is a multicentre, double-blind, randomised, placebo-controlled, parallel-group trial in patients with acute intracerebral haemorrhage with a CAVE score \geq 3 or an acute ischaemic stroke with a SeLECT score \geq 6.

At the first visit (screening/baseline, V1a), patients will undergo several examinations to check eligibility. The next visit (V1b) has to be performed within 96 hours after primary stroke occurrence. After eligibility has been confirmed, patients will be randomised (randomisation ratio 1:1) to treatment with ESL 800 mg (Group A) or placebo (Group B). Patients can receive therapies for stroke treatment according to local clinical practice at any time during the trial.

Patients will start treatment with the investigational medicinal product (IMP), i.e. ESL or placebo, within 96 hours after primary stroke occurrence at V1b. They will continue treatment until Day 30 after randomisation and then be tapered off. Thereafter, patients will be followed up until 18 months after randomisation. Patients can concomitantly receive antiepileptic therapies, except commercially available ESL or oxcarbazepine, until Day 30. Concomitant antiepileptic therapies have to be discontinued and down-titration has to be started according to the respective Summary of Product Characteristics (SmPC). If the antiepileptic drugs (AEDs)/benzodiazepine are not already discontinued before, down-titration must be started on Day 31 at the latest.

If one or more AS(s) occur(s) within 7 days after primary stroke, this will not result in change of IMP dose. Patients having a first US will discontinue IMP treatment and will be treated at the discretion of the investigator until 18 months after randomisation, except with commercially available ESL.

Further visits will be performed 7 days (V2, on-site), 37 days (V3, on-site), 12 weeks (V4, telephone), 26 weeks (V5, on-site), 38 weeks (V6, telephone), 52 weeks (V7, on-site), 64 weeks (V8, telephone) and 78 weeks (End of Trial [EoT] visit, on-site) after V1b. Patients

who discontinue trial participation prematurely will be asked to come to the site for an early discontinuation visit (EDV). Unscheduled visits (UNS) will be performed at the discretion of the investigator, as necessary.

Patients or their caregivers (as applicable) will be instructed to contact the site immediately after a seizure has occurred and to document seizure information in the patient diary.

Number of patients (planned):

Screened:	220
Randomised:	200

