14. ECG
15. Suicidal ideation and behaviour (as per PHQ-9, question 9)

Exploratory endpoint:

16. EEG, optional

Statistical methods:**Analysis sets:**

- Enrolled set (ES): All patients enrolled into this trial.
- Safety set (SS): All patients who were randomised and were treated with at least one dose of IMP (ESL or placebo). Patients will be assigned to treatment groups as treated.
- Full analysis set (FAS): All patients who were randomised and were treated with at least one dose of IMP (ESL or placebo). Patients will be assigned to treatment groups as randomised.
- Per protocol set (PPS): All patients of the FAS without major protocol deviations. Patients will be assigned to treatment groups as treated.
- EEG analysis subset: All patients in the FAS with a baseline and a post-baseline EEG recording available.

The primary hypotheses will be assessed in the FAS by means of a chi-square test with continuity correction on the significance level of 5% (two-sided).

Secondary efficacy analysis includes an analysis of the proportion of patients who experience the first US within the first 12 and within 18 months after randomisation (12 months and 18 months failure rate, respectively), time to first US after randomisation as well as time to first US after stroke by means of Kaplan-Meier estimate, and cause-specific cumulative incidence curves to evaluate the competing risk in case of deaths before the first US, as well as descriptive statistics for number of AEs, number and 4-week rate of USs, the BI, the NIHSS score, the PHQ-9.

EEG parameters will be evaluated exploratively using descriptive statistics.

Safety analysis will focus on the presentation of TEAEs by system organ class (SOC) and preferred term (PT), and the analysis of vital signs, safety laboratory data, ECG, physical and neurological examination, and suicidal behaviours assessed using PHQ-9.

Sample size estimation: Based on historical data, 26% of patients are expected to experience the first US within the first 6 months after stroke (i.e. failure rate) with standard of care. As this is a pilot trial, no empirical estimate of the treatment effect in patients randomised to ESL is available. For the purpose of sample size estimation, the trial is planned to have at least 80% power to demonstrate a significantly lower failure rate under ESL (Group A) compared to placebo (Group B) under the following assumptions:

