- An expected failure rate (including death before the first US) of 26% under placebo within the first 6 months after stroke.
- An expected failure rate (including death before the first US) of 8% under ESL within the first 6 months after stroke.
- In order to account for a missing data rate of 5% for reasons other than death before the first US, in each treatment arm, the sample size calculated on adjusted failure rates (including missing data) of 29.7% under placebo and 12.6% under ESL, respectively.

Under these assumptions 100 randomised patients per treatment arm will ensure a power of the trial of at least 80% to demonstrate a significantly lower failure rate under ESL compared

to placebo by means of a two-sided chi-square test with continuity correction on a 5%-level of significance.

Assuming that the failure rate in missing observations equals the failure rate with placebo for both treatment groups, the power of the trial is 87%. Based on the expected failure rates without adjustment for missing data, the power of the trial is 89%.

Schedule of trial procedures

Visits	V1a ²	V1b ²	V2 ¹⁵	V3 ¹⁵	V4	V5	V6	V7	V8	EoT ¹²	EDV ³	UNS ¹
Days / Weeks after V1b			+7 days	+37 days	+12 weeks	+26 weeks	+38 weeks	+52 weeks	+64 weeks	+78 weeks		
On-site visit ☺/telephone contact ☎	☺	☺	☺	☺	☎	☺	☎	☺	☎	☺	☺	☺/☎
Day	-3 to -1	1 (within 96 h after stroke)	8±2	38±4	85±10	183±10	267±10	365±10	449±10	547±10		
Initiation procedures												
Informed consent	● ⁹			● ¹⁰							(●) ¹⁴	
Demographics	●											
Medical history	●			● ¹⁰							(●) ¹⁴	
Prior medication	●			● ¹⁰							(●) ¹⁴	
Concomitant medication	●	●	●	●	●	●	●	●	●	●	●	●
SeLECT score/CAVE score ¹¹	● ⁴											
Modified Rankin Scale (mRS)	● ⁴											
Inclusion/exclusion criteria	●	●	● ¹⁰									
Randomisation (1:1)		●										
Medication												
First investigational medicinal product (IMP) administration		●										
Dispense IMP		●									(●)	
IMP accountability				●							● ¹³	(●)
Efficacy												
Issue diary (seizures)	●		●	●		●		●			(●)	
Review and collect diary		● ⁸	●	●		●		●		●	●	(●)
Seizure screening questionnaire	●	●	●	●	●	●	●	●	●	●	●	●
Record seizures (diary/questionnaire) ¹⁶	●	●	●	●	●	●	●	●	●	●	●	●
Barthel Index (BI)	●			●		●		●		●	●	(●)
National Institutes of Health Stroke Scale (NIHSS)	● ⁴		●	●		●		●		●	●	(●)
Patient Health Questionnaire (PHQ-9)	●			●		●		●		●	●	(●)
Electroencephalogram (EEG, optional) ⁵	(● ⁴)									(●)		(●)

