### **5.5.2.3 Time to First Unprovoked Seizure after Randomisation**

For the following analyses, patients will be censored at their last day in the trial.

The time to first US after randomisation will be analysed and presented by means of the Kaplan-Meier estimate (including censored data e.g. withdrawals) after 6, 12 and 18 months for the failure time and corresponding simultaneous CI, a log-rank test (p-value) as well as estimates for 25% percentile, median, and 75% percentile failure time and corresponding CI. The time to first US will be analysed from the day of randomisation.

For this purpose, the following SAS code will be used:

```
ODS OUTPUT Quartiles=quartiles;
ODS OUTPUT ProductLimitEstimates=limit;
ODS OUTPUT HomTests= tests;
PROC LIFETEST DATA=<dataset> METHOD=KM CONFBIAS=EP TIMELIST= 182 365 547;
  TIME <Time to first US>*<Status> (0);
  STRATA <Treatment group> /TEST=LOGRANK;
RUN;
```

The Kaplan-Meier product limit estimate and simultaneous equal precision 95% confidence bands will be graphed.

In case of deaths before the first US, the competing risk of deaths and US will be evaluated exploratively using cause-specific cumulative incidence function and Gray's test for homogeneity in addition.

The following SAS code will be used:

Note: the status will be 0 for censored observations, 1 if US occurred and 2 if the patient died before experiencing an US.

```
ODS OUTPUT GrayTest= graytest;
```

```
PROC LIFETEST DATA=<dataset>;
  TIME <Time to first US or death>*<Status> (0) /eventcode=1;
  STRATA <Treatment group> / order=internal;
RUN;
```

The following statistical outputs will be presented:

Table 15.2.5.1.1 Time to First Unprovoked Seizure after Randomisation– Full Analysis Set

Table 15.2.5.1.2 Time to First Unprovoked Seizure after Randomisation – Per-Protocol Set

The time to first US after randomisation will be presented by estimates for 25% percentile, median, and 75% percentile failure time and corresponding CI; means of the Kaplan-Meier estimate after 6, 12 and 18 months for the failure time and corresponding simultaneous CI (equal precision bands) and the p-value of a log-rank test

Figure 15.2.1.2.1 Time to First Unprovoked Seizure after Randomisation – Full Analysis Set

Figure 15.2.1.2.2 Time to First Unprovoked Seizure after Randomisation – Per-Protocol Set

The Kaplan Meier Product Limit Estimate and simultaneous equal precision 95% confidence bands will be presented for the treatment groups.

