**Note: Data should be sorted by treatment group (first “ESL” then “Placebo”)**

```
proc npar1way hl correct=no alpha=.05 data=<dataset>;
  class <treatment_group>;
  var <change from baseline of BI_total_score at specific timepoint>;
  exact wilcoxon;
  exact hl;
  ods select WilcoxonScores WilcoxonTest HodgesLehmann;
run;
```

If this SAS code runs for more than 10 minutes, maxtime=50 will be used and the normal approximate result will be tabulated. A higher maxtime does not lead to a change of the result.

Cumulative incidence of USs will be illustrated using Kaplan-Meier curves by the BI Baseline categories (<=79, 80-100) and treatment group. Patients without an event or lost to follow-up will be censored at their last visit or termination date. Time to event will be calculated from time of randomisation to first US.

The following statistical outputs will be presented:

[Table 15.2.6.1.1 Summary of Barthel Index Total Score – Full Analysis Set](#)

[Table 15.2.6.1.2 Summary of Barthel Index Total Score – Per-Protocol Set](#)

The default summary statistics for the BI total score will be presented by visit slots by treatment group at Baseline, V3, V5, V7, EOT, EDV (if applicable) and Endpoint.

[Table 15.2.6.2.1 Analysis of Barthel Index Total Score Differences – Full Analysis Set](#)

[Table 15.2.6.2.2 Analysis of Barthel Index Total Score Differences – Per-Protocol Set](#)

The Hodges-Lehmann estimate of location shift and the corresponding 95% CIs including the Wilcoxon Mann Whitney test p-value will be presented by visit slots for V3, V5, V7 and Endpoint for ESL-Placebo.

[Figure 15.2.2.1 Cumulative Incidence Curves of Unprovoked Seizures using Kaplan-Meier Curves by Barthel Index Total Score – Full Analysis Set](#)

[Figure 15.2.2.2 Cumulative Incidence Curves of Unprovoked Seizures using Kaplan-Meier Curves by Barthel Index Total Score – Per-Protocol Set](#)

Cumulative incidence curves of USs using Kaplan-Meier curves displayed by time of randomisation and treatment group for each category of the BI total score.

[Listing 16.2.3.3 Barthel Index – Enrolled Set](#)

The BI items and total score data will be listed by treatment group.

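### Six figures labelled cumulative incidence of unprovoked seizures are Kaplan-Meier curves that censor deaths, and the planned competing-risk results have no numbered output

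*SAP*

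**What the plan says.** SAP 5.5.2.6 (NIHSS): "Cumulative incidence of USs will be illustrated using Kaplan-Meier curves by the NIHSS baseline categories". SAP 5.5.2.5 (Barthel Index): "Cumulative incidence of USs will be illustrated using Kaplan-Meier curves by the BI Baseline categories". Both sections split the curves further by treatment group and censor anyone without an event, or lost to follow-up, at the last visit or termination date. Neither gives death its own status. SAP 5.5.2.7 (PHQ-9) also calls its curves cumulative incidence and titles them as Kaplan-Meier. It does not restate a censoring rule. The figures concerned are 15.2.2.1, 15.2.2.2, 15.2.3.1, 15.2.3.2, 15.2.4.1 and 15.2.4.2.

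SAP 5.5.2.3 handles death differently. If deaths occur before a first US, the two competing risks are to be explored "using cause-specific cumulative incidence function and Gray's test for homogeneity in addition". Its code sets US to 1 and death before a US to 2, and compares the treatment groups. The protocol synopsis (Statistical methods) also plans cause-specific cumulative incidence curves.

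The outputs described under 5.5.2.3 are Tables 15.2.5.1.1 and 15.2.5.1.2 (Kaplan-Meier estimates, quartiles, log-rank p-value) and Figures 15.2.1.2.1 and 15.2.1.2.2 (Kaplan-Meier with confidence bands).

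**The concern.** With death as a competing event, one minus Kaplan-Meier is not the cumulative incidence. It estimates the seizure risk in a hypothetical population in which nobody dies first. The SAP therefore uses one term for two quantities: a true cumulative incidence function in 5.5.2.3, and a Kaplan-Meier complement in 5.5.2.5 to 5.5.2.7.

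These figures invite comparison between baseline categories. If death before a US is commoner in one category, its curve is inflated more than the other, and part of the visible gradient comes from the method.

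The second issue needs no mortality assumption. An analysis named in the protocol and coded in the SAP has no place in the reported outputs, so it could go unreported without being declared dropped.

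**Working it through.** **1. The plan's own figures.** The documents give no figure for these curves. The nearest are the 6-month rates in the protocol's sample size estimation: "An expected failure rate (including death before the first US) of 26% under placebo within the first 6 months after stroke" and "An expected failure rate (including death before the first US) of 8% under ESL within the first 6 months after stroke". The protocol adds a "missing data rate of 5% for reasons other than death before the first US". Counting missing patients as failures gives 0.95 × 0.26 + 0.05 = 0.297 and 0.95 × 0.08 + 0.05 = 0.126. These match the stated 29.7% and 12.6%. With the continuity-corrected chi-square test, 80% power needs 100 per arm, as stated. So the 26% already contains deaths, but its split between US and death is not given.

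**2. Formulas.** Let x be one minus Kaplan-Meier for US at time T, and d the corresponding net risk of death. Assume independent hazards.

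- Cumulative hazards: A = −ln(1 − x) and B = −ln(1 − d).
- With constant hazards, cumulative incidence (CIF) = A/(A + B) × (1 − exp(−(A + B))).
- If every death came on Day 1, CIF = x(1 − d), so the gap is x·d. This is the largest gap possible for given x and d.

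**3. Arm-level gap at 6 months, placebo.** Holding US plus death at 26% means (1 − x)(1 − d) = 0.74.

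- Equal split: x = d = 1 − √0.74 = 0.140.
- Constant hazards: CIF = 0.5 × 0.26 = 0.130. The gap is 0.140 − 0.130, about 1.0 point. Varying the split does not raise it above about 1.0 point.
- All deaths on Day 1: the gap is 0.140 × 0.140 = 0.020, or 2.0 points. This is the maximum over all splits.

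For ESL at 8%, √0.92 = 0.959, so x = d = 0.041 and the Day 1 maximum is 0.041² = 0.0017, under 0.2 points.

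**4. Possible gap in one category at 18 months.** Both the US risk and the death risks here are assumptions, because no section gives either by category. Constant hazards:

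| Assumed net death risk | CIF if 1−KM = 26% | Gap (points) | CIF if 1−KM = 40% | Gap (points) |
|---|---|---|---|---|
| 0% | 26.0% | 0 | 40.0% | 0 |
| 5% | 25.4% | 0.6 | 39.1% | 0.9 |
| 10% | 24.7% | 1.3 | 38.1% | 1.9 |
| 20% | 23.4% | 2.6 | 36.2% | 3.8 |
| 30% | 22.1% | 3.9 | 34.2% | 5.8 |
| 40% | 20.6% | 5.4 | 32.0% | 8.0 |

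Worked row (26%, 30%): A = 0.301 and B = 0.357. CIF = 0.301/0.658 × (1 − 0.74 × 0.70) = 0.458 × 0.482 = 0.221.

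Two categories with the same 26% curve but 5% and 30% deaths would have actual risks of 25.4% and 22.1%.

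**5. Output lists.** SAP 10.1 (tables) and 10.3 (14 figures) contain no entry for a cumulative incidence function or Gray's test. The code in 5.5.2.3 saves the Gray's test result to a dataset that no listed output uses. SAP Section 8 records two deleted secondary endpoints and does not mention the competing-risk analysis.

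**The case against.** The strongest case against has four parts.

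- **The figures only illustrate.** No test or estimate is attached, and every title says Kaplan-Meier. Kaplan-Meier with deaths censored is a recognised display of net risk, so the fault lies in the label. This stands, and it is why relabelling is an acceptable minimum.
- **Sampling error is larger than the arm-level gap.** Recruitment stopped short of 200. Four curves per figure, if evenly split, means fewer than 50 patients each. At 26% the standard error is then at least √(0.26 × 0.74/50) = 6.2 points. This limits the practical harm but does not make the label correct.
- **Other outputs show the treatment comparison with deaths kept in the denominator.** Tables 15.2.1.5.1 to 15.2.1.5.6 count only observed USs as failures, by arm, at 6, 12 and 18 months. The failure-rate tables split failures into US, death, withdrawal and missing, and overall survival is reported by arm. So it would be wrong to infer that the reader gets no view of treatment effect allowing for death. However, those tables also count dropouts as non-failures, and none is by Barthel, NIHSS or PHQ-9 category.
- **The analysis is still planned.** Both documents commit to it, and the SAP makes it exploratory and conditional on deaths occurring. The table and figure shells are separate attachments that were not available. The finding is therefore an omission from the SAP's own output lists, not proof that the analysis was abandoned.

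**Conclusion.** The point holds as one of labelling and output specification. The six figures do not show the quantity they name if anyone dies before a US, and the error is always upward. Its size is unknown. At arm level at 6 months it is about 1 point with constant hazards and at most about 2 points, given the protocol's 26% for US plus death and independent hazards. It could reach several points by 18 months in a category with high mortality, and it is zero with no deaths.

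Two stronger readings are tempting and not supported:

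- **That the overstatement is greatest in the severe groups.** This requires more deaths before US in those groups. It is plausible for NIHSS of 11 or more and Barthel of 79 or less, but no section gives mortality by category. PHQ-9 above 4 is a depression category, not a stroke-severity group.
- **That 26% is a seizure-only risk to which 10% to 30% deaths can be added at 6 months.** At 30% this implies combined failure of 1 − 0.74 × 0.70 = 48%, against the protocol's 26% including death.

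The primary analysis, a "chi-square test with continuity correction on the significance level of 5% (two-sided") with deaths counted as failures, does not use these curves and is unaffected. So is the sample size.

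**What to change.** 1. Draw Figures 15.2.2.1 to 15.2.4.2 with the cumulative incidence function, using the coding in SAP 5.5.2.3 (US = 1, death before US = 2, censored = 0). At minimum, retitle them as one minus Kaplan-Meier with deaths censored. State the censoring rule in 5.5.2.7 as well.
2. Add cumulative incidence of US at Day 182, 365 and 547, and Gray's p-value, to Tables 15.2.5.1.1 and 15.2.5.1.2.
3. Add a numbered cumulative incidence figure by treatment group to SAP 10.3. If the analysis is not to be reported, say so in Section 8.

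The cost is small: the code is already in the SAP, and the additions are a few table rows and one figure per analysis set.
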